4.8.1. AI man aged 50-75 years old

4.8.2. AI woman aged 21-75 years old

4.9. Inclusion Criteria for Aim 8 – Pilot Testing of the Interventions

4.9.1. For the Breast Cancer Intervention: AI women age 50-75, average risk for breast cancer, and never had a mammogram OR not had a mammogram within the past 2 years.

4.9.2. For the Colorectal Cancer Intervention: AI men and women aged 45-75, average risk for CR cancer, and never had a fecal occult blood test (FOBT), or fecal immunochemical test (FIT) or a colonoscopy OR not had a FOBT or FIT in the past year, OR no colonoscopy in the past 10 years.

4.9.3. For the Cervical Cancer Intervention: women aged 21-75, never had a cytology (Pap smear) OR had a Pap smear more than 3 years ago OR women aged 30-75, and never had screening with a combination of cytology and human papillomavirus testing OR no combination of testing in the past 5 years.

4.10. **Exclusion Criteria**

- 4.10.1. Cognitively impaired adults are excluded from participation
- 4.10.2. Adults not able to consent for themselves are excluded from participation
- 4.10.3. Prisoners may not participate in this study

5. Number of Subjects

5.1. Aim 3

- 5.1.1. Aim 3 is formative and therefore the sample size is not guided by a power analysis. For each of the up to 21 focus groups (until we reach thematic saturation), N=12-15 eligible persons will be invited, with the expectation that on average N=8-12 will attend. Since this is a community-based participatory study, we will not turn away any eligible person who show up for the focus group. Thus, we seek approval for including 150 AI men and women for the focus group.
 - 5.1.1.1. *Focus Groups Among Women aged 50-75 on Cancers of Breast, Colon-Rectum, and Cervix*: up to 5 Focus Groups, or until we reach thematic saturation (participants: N=60-75)
 - 5.1.1.2. *Focus Groups Among Men aged 50-75 on Cancers of the Colon-Rectum and Prostate*: up to 5 Focus Groups, or until we reach thematic saturation (participants: N=60-75)
 - 5.1.1.3. *Focus Groups Among Women aged 21-49 on Cervical Cancer*: up to 5 Focus Groups, or until we reach thematic saturation (participants: N=60-75)
 - 5.1.1.4. *Focus groups with Tribal Advisory Panel (TAP) members*: up to 3 Focus Groups, or until we reach thematic saturation (participants: N=36-45- total)
 - 5.1.1.5. *Healthcare Provider focus groups*: up to 3 Focus Groups, or until we reach thematic saturation (participants: N=36-45 total)

5.2. Aim 4

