- 5.2.1. Aim 4 is to conduct surveys with approximately N=250-280 eligible AI men and women.
 - 5.2.1.1. *Survey on Cancer of the Cervix (Women aged 21-49)*: N=50-60 AI women
 - 5.2.1.2. *Survey on Cancers of the Colon-Rectum, Breast, and Cervix (Women aged 50-75)*: N=100-110 AI women
 - 5.2.1.3. *Survey on Cancers of the Colon-Rectum and Prostate (Men aged 50-75)*: N=100-110 AI men

5.3. Aim 7

- 5.3.1. Aim 7 is to develop the interventions, including the small media, with about 12-15 TAP members (section 4.5) and 150 eligible AI men and women (we will invite 12-15 participants

in up to 15 total focus groups, with expectation that on average we will have 8-10 participants will attend) (section 4.8)

5.4. Aim 8

5.4.1. Aim 8 is to test the three interventions with about up to 150 eligible participants

Total between the Aims: N=706-850 participants

6. Study Timelines

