Because of participant and TAP member request following the focus groups, we will be mailing out the 3 brochures (breast, cervical, and colorectal) to all postal mailboxes in the Pueblo of Zuni prior to the intervention. There is one post office in the Pueblo that serves the households of Zuni, where all mail for residents are delivered. The study team will work with a local printer that will print and mail these brochures to each occupied (active) mailbox at the Zuni post office, approximately 1,530 mailboxes. We will not request any identifiable information from the tribe to complete this mailing rather we will use a method of mass mailing that will direct the mailout to “postal customers”, where the postmaster will deliver these brochures to active mailboxes in the Zuni Pueblo and appropriate zip code.

Aim 8: Pilot test (including qualitative methods) the multilevel/ multicomponent culturally and linguistically appropriate intervention strategies on outcomes such as: impact on screening practices; feasibility of implementation and acceptability of the intervention; and cost effectiveness of the intervention.

We will pilot test the intervention (INT) to document its: impact on screening practices; feasibility/acceptability; promoters/barriers to screening; effect positive changes on the MHOF constructs; and cost effectiveness. We will use quantitative followed by qualitative (focus group) mixed methods. We will recruit participants based on gender and age for cancer-specific screenings. In all, we will have up to 60 men age 45-75 (for CR cancer INT) 60 women age 45-75 (for breast [50-75 only], CR, and cervical cancer INTs) and 30 women age 21-44 (for cervical cancer INT). We will offer each group the specific cancer INT(s).

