Implementation of quantitative (survey) data collection to document INTs' impact on screening. We will contact (in-person or phone call) interested participants and provide them with a study description (StudyDescription_Intervention_2022_10_26_V1). If participants are interested, the study will continue with eligibility (Eligibility_Screener_Intervention_2023_02_02_V2). If participants are eligible, they will provide contact information (ContactSheet_Intervention_2022_10_26_V1) for the purposes of scheduling the study activities. The study will provide a packet that will contain the consent letter (ConsentLetter_InterventionTesting_2023_02_02_V4) that describes the study, PI contact information, description of the overall benefits and risks of participation, and dates for the study activities (i.e., baseline [BL] survey, INT session, post-intervention survey). The contact sheet will also ask participants if they wish to be contacted for future studies. If participants wish to be contacted, this will form our convenience sample for recruitment for the qualitative data collection for Aim 8 (focus groups). We will be using a consent letter format to continue to minimize COVID-19 exposure and risks for both community members and study team. The study is also minimal risk (surveys and educational session on specific age-gender cancer through the use of cancer specific flipcharts and small media) and encourages standard of care. The packet will also contain a scheduling card to inform participants about the date and time for the next project activity (baseline survey, INT session, post-intervention survey, focus group). Zuni students and staff will administer the surveys. We will conduct 2 waves of outcomes evaluation surveys: BL and at follow-up (6-8 months post-INT). [NOTE: We will submit the surveys to the HRRC and SWTIRB for review and approval prior to conduct of the surveys.]

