13.1. The patient questionnaires will be analyzed utilizing approaches consistent with each data source. The structured questions will be exported from REDCap to a statistical software package for analysis. The qualitative responses to the questionnaire will be digitally recorded and transcribed for standard content analysis. The UNMCCC's Behavioral Measurement and Population Science Shared Resource will support the qualitative and quantitative data analysis efforts.

13.2. Quantitative Data Analysis (Aims 4 and 8): We will use descriptive statistics to characterize participant characteristics and their knowledge, attitude, screening practices, and preferred intervention strategy. We will use univariable and multivariable logistic regression analyses, with inclusion of modeling variables informed by the MHOF, to assess the relationship between socio-demographic variables, knowledge, and attitudes and beliefs on screening behaviors (Aim 4).

For Aim 8, for the primary outcome (completion of cancer screening), we will compare the number of cancer screening approaches (i.e., screenings for breast, CR, and/or cervical cancers) undertaken by study participants (based on age and gender), offset by the number of possible screening tests, using Poisson regression approaches between those who are and are not receiving active intervention. This will enable the estimation and comparison of screening uptake between treatment arms, even when there are different numbers of possible screening tests for groups of participants. We will account for within-cluster correlations using generalized estimating equations, and we will explore the impact on screening uptake of patient characteristics (e.g. sex) using fixed effects.

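### Aim 8: Section 13.2 needs an untreated group that Section 12 never creates, and baseline cannot fill that place because eligibility fixes its value for every test due

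*Combined protocol and SAP*

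**What the plan says.** **Who enters (Section 4.9).** The breast criterion is "AI women age 50-75, average risk for breast cancer, and never had a mammogram OR not had a mammogram within the past 2 years". The colorectal criterion covers people never tested and then adds "OR not had a FOBT or FIT in the past year, OR no colonoscopy in the past 10 years". The cervical criterion has a cytology route and, from age 30, a route for women who "never had screening with a combination of cytology and human papillomavirus testing OR no combination of testing in the past 5 years".

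**What they receive (Section 12, Aim 8).** Each age and sex group is offered the intervention for its cancer or cancers. No control group, allocation step or delayed start is described. Section 5.4.1 gives the size: "Aim 8 is to test the three interventions with about up to 150 eligible participants". Section 12 splits it: "In all, we will have up to 60 men age 45-75 (for CR cancer INT) 60 women age 45-75", plus 30 women aged 21-44.

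**What is measured (Section 12, Aim 8).** Under a heading about documenting impact on screening: "We will conduct 2 waves of outcomes evaluation surveys: BL and at follow-up (6-8 months post-INT". Sections 6.4.1 and 7 put the follow-up survey at 12 months instead.

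**How it is analysed (Section 13.2).** The primary outcome is the number of screening tests undertaken, offset by the number possible, compared "using Poisson regression approaches between those who are and are not receiving active intervention". Generalized estimating equations handle within-cluster correlation, and the text refers to treatment arms.

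**The concern.** The model in Section 13.2 needs observations from people not receiving the intervention. In the Aim 8 procedures, the only such observations are each participant's own answers before the session. An analyst following the plan would therefore be drawn to use baseline as the untreated side.

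For a test that is due, eligibility has already set the baseline answer to not done. The difference can then only stay at zero or rise. The criteria also admit people only just past an interval, such as someone whose last FIT was 13 months ago, and some of these would return without any programme. The brochures mailed to about 1,530 mailboxes before the intervention could add uptake that does not come from the sessions. A rise would show that some overdue people were screened. It would not show that the intervention caused it, and impact on screening practices is the first outcome listed for Aim 8.

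**Working it through.** **1. The plan's own figure.** The groups in Section 12 sum to 60 + 60 + 30 = 150, which matches Section 5.4.1. No significance level, power, effect size or dropout rate is given for Aim 8, so there is nothing further to reproduce.

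**2. Assumptions, none of them in the documents.** The intervention has no effect. Nobody has the test at baseline. A proportion *b* of overdue people would be screened by follow-up anyway. Baseline and follow-up are compared by an exact McNemar test at two-sided 0.05. The documents give no value for *b*, so a range is shown.

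**3. When the test is significant.** With a zero baseline every discordant pair is a gain, so with *k* gains p = 2 × 0.5^*k*. Five gains give 0.0625 and six give 0.031. Six gains are enough, whatever the sample size.

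**4. Chance of a significant rise with no effect.** This is P(X ≥ 6) for X ~ Binomial(N, *b*):

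| N | *b* = 2% | 5% | 10% | 20% |
|---|---|---|---|---|
| 150 (all groups) | 8% | 77% | 99.8% | about 100% |
| 120 (150 less 20% loss) | 3% | 56% | 98% | about 100% |
| 60 (men, or women 45-75) | 0.1% | 8% | 56% | 99% |
| 30 (women 21-44) | <0.1% | 0.3% | 7% | 57% |

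At N = 150 the chance is 30% at *b* = 3% and passes 50% at about 3.8%.

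**5. Size of the apparent gain.** The expected rise equals *b*: 3, 7.5, 15 and 30 people of 150 at 2%, 5%, 10% and 20%. Some rise, significant or not, appears with probability 1 − (1 − *b*)^N. For N = 60 and *b* = 5% that is 1 − 0.95^60 = 95%.

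**6. Is a zero baseline right?** For anyone enrolled under the breast criterion, yes. The colorectal and cervical criteria are joined by OR. Read literally, they admit a person with a colonoscopy inside 10 years but no FIT in the past year, or a woman aged 30 or over with a recent Pap smear but no co-test in 5 years. If a share *q* is current at baseline and a proportion *r* of those lapse, the expected net change is (1 − *q*)*b* − *qr*. With *q* = 20% and *b* = 10% (N = 150, 20,000 simulated trials per row):

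| *r* | Net change | Chance of a significant rise |
|---|---|---|
| 5% | 0.08 − 0.01 = +0.07 | 81% |
| 15% | 0.08 − 0.03 = +0.05 | 37% |
| 30% | 0.08 − 0.06 = +0.02 | 6% |

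With *q* = 40%, *b* = 5% and *r* = 15% the net change is 0.03 − 0.06 = −0.03, and any observed rise occurs in only 8% of runs. The one-way bias therefore belongs to tests due at baseline, not to overall up-to-date status.

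**7. With a real concurrent group.** Take 75 against 75 (an assumed split), the same background uptake in both, no effect, and Fisher's exact test at 0.05. The chance of a significant difference in favour of the intervention is 0.7%, 1.3% and 1.6% at *b* = 5%, 10% and 20%. The problem arises from using baseline as the comparator, not from enrolling overdue people.

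**The case against.** The strongest reply is that Section 13.2 specifies no before-after test of screening. It names a Poisson comparison between arms, and no McNemar test or significance level appears for Aim 8. The baseline survey also has another use, since Aim 8 looks for change on the MHOF constructs. The outcome in 13.2, tests undertaken over tests possible, is already close to follow-up uptake. And with a genuine concurrent group the bias would not drive the primary result. All of this stands, so the point is conditional on baseline being used as the untreated side. The reply does not say who else could fill that side.

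A reader might infer more than the documents support:

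- **That the plan has committed to a before-after test that will come out positive almost regardless of effect.** It has not. The probabilities depend on a background rate that the documents do not give and on N, which is stated only as a maximum. In the smaller groups they are low at 5% background.
- **That baseline uptake is fixed near zero for all three cancers.** Only the breast criterion guarantees this. Lapses among people current by another test can shrink or reverse the overall change.
- **That the 13.2 rate ratio has no finite value.** This would follow only from fitting the model to baseline against follow-up with an all-zero baseline, which 13.2 does not prescribe.

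The eligibility screener and survey instruments are cited but not included, so how baseline screening is recorded cannot be checked.

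**Conclusion.** The point holds in conditional form. Section 13.2 requires an untreated group, Section 12 supplies none, and the one substitute within Aim 8 has its value set by eligibility for every test due. A rise from that baseline cannot separate an intervention effect from ordinary return to screening.

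Under the assumptions listed, the chance of a spurious significant rise in 150 people goes from 8% at 2% background uptake to 99.8% at 10%. At 5% background it is 77% for 150 people, 8% for 60 and 0.3% for 30. These figures show how sensitive the reading is; they do not predict the pilot's result. The direction of the bias, for tests due at baseline, does not depend on the test or the significance level chosen.

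**What to change.** 1. In Section 13.2 and Section 12 (Aim 8), state that baseline screening status defines eligibility and the tests due, and is not a comparator.
2. If a concurrent untreated group exists, describe it: who they are, how they were allocated, and when they are offered the intervention. Otherwise replace the between-arm comparison with follow-up uptake among tests due at baseline, with the number of tests due as the offset. Report it overall and by age and sex group with 95% confidence intervals, keeping the GEE so that several tests from one woman are not treated as independent.
3. Report the result as uptake after the intervention, not as impact.
4. Keep before-after comparisons for the MHOF constructs, on which nobody is selected.
5. Reconcile the 6-8 month and 12-month follow-up, since a longer window lets more background screening accumulate.

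An aggregate background rate from the health center may be shown as context, but not as a threshold for claiming an effect. Aim 8 enrols convenience volunteers on self-report (Sections 4.1 and 20.1), who may exceed a clinic rate with no intervention effect. Section 12 also reports responses to a post-intervention survey question, so a threshold may no longer be one set in advance.

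The cost is wording and a simpler analysis, with no extra participants. The pilot gives up an effect claim on screening. It keeps a usable estimate: with one test due for each of 150 people, 20% uptake would have a Wilson 95% interval of 14.4% to 27.1%, and 30% uptake 23.2% to 37.8%.

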This approach effectively addresses mistrust of research and researchers through establishing a non-hierarchical partnership model^{19,20}. CBPR is used successfully to address a variety of health priorities^{19,20} and is a necessary research methodology with AIs³³⁻³⁶. We will constitute an Advisory Panel comprising stakeholders representing Zuni community members and CHRs, cancer survivors, IHS healthcare providers, and researchers. The Panel will actively participate in the research, including finalization of the study aims, research design and approach, recruitment strategies, development of data collection instruments, and constituency checking of data inferences. We will (1) build on the various stakeholders' strengths, and integrate our respective knowledge and expertise and (2) support an inter-dependent partnership, with a long-term commitment for mutually beneficial co-learning and capacity enhancement. The Panel will comprise nine members and will meet every six months or more often if necessitated. Panel members will receive \$100 for their participation and contributions.

4. Inclusion and Exclusion Criteria

- 4.1. People will be screened for eligibility for the respective sub-projects (Aims 3, 4, 7, and 8) by trained staff. Participants who meet the inclusion criteria for the sub-projects, as defined below according to self-report on the screening form, will be invited to participate in the respective part of the study.

4.2. Inclusion Criteria for Aim 3 – AI Female Aged 50-75 Year Focus Groups

4.2.1. *Criteria for Focus Groups on Cancers of the Breast, Colon-Rectum, and Cervix:*

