We will administer BL and post-INT surveys in-person or over the phone and each will last approximately 20-30 minutes, dependent on the cancer specific survey (Baseline Survey_Men45-75_2023_02_02_V2, Baseline Survey_Women21-49_2023_02_02_V2, Baseline Survey_Women50-75_2022_10_26_V1, PostIntervention_Survey_Men45-75_2023_04_28_V1, PostIntervention_Survey_Women21-44_2023_04_28_V1, PostIntervention_Survey_Women45-75_2023_04_28_V1). Prior to each project activity, we will contact (phone or in-person) participants informing them of the date, time and place of the upcoming activity. During each project activity, we will confirm/update the participants' contact information. Between 6-8 months post-INT, we will remind (phone or in-person; at 3-monthly intervals), if necessary, participants to complete their screening exam. Participants that report completing their appropriate screening will be taken off the reminder call list.

For post-INT follow-up with participants starting at 6 months, they will be contacted by phone (either text or phone call) once a week over the course of three weeks. If no response from phone outreach, then two home visits will be made, over the course of two weeks. If participant does not respond after the two home visits, a note will be left for the participant with study team contact information (Intervention_participant note_2023_06_30). Following this, no further contact will be attempted to the participant from the study team. The participant will have until the end of their 8th month to complete their post-INT follow-up survey.

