Multilevel/multicomponent INT. The TAP will finalize the INT strategies (Aim 7). The overall INT will be bounded by contextual realities (rurality of the Zuni Pueblo, resources at the health center, budget for the project). With this context in mind, we could operationalize The Community Guide's recommended strategies that the TAP may plausibly identify as follows: To increase community access, we could: (a) Identify a point-person (i.e., Public Health Nurse) at the health center who will triage participants to and schedule them for appropriate screening(s). (b) Remind (phone or in-person) participants (between post-INT and follow-up) to complete their screening exam(s), offer assistance in

scheduling a screening appointment and a ride to the health center. These strategies would reduce administrative barriers, navigate participants, and assist with transportation and in scheduling an appointment. To increase community demand, we could consider: (a) Small media. (b) 1-on-1 education (supplemented by the small media) by the project's staff. (c) Reminders between post-INT and follow-up. (d) Cognitive-behavioral group education and incentives. To increase provider delivery, we could: (a) Reduce health center-specific systemic barriers by identifying a point-person to promote and facilitate screening services.

Implementation of the INT. We will implement the INT over a 1-hour long session following the BL. The INT session will consist of an educational session that is approximate 1-hour long, dependent on the cancer and will be conducted in-person with COVID-19 safety precautions. This educational session will use flipcharts that teach participants about a specific cancer, risks, protective factors, cancer specific screening, stages of cancers and survival (Breast Cancer Flipchart 2022_10_26_V2, Cervical Flipchart_2022_10_26_V2, Colorectal Flipchart_2022_10_26_V2). The flipcharts will be accompanied by the small media documents, factsheets and brochures (previously HRPO approved).

Cancer screening, analysis, reporting, and follow-up of test results. The health center will analyze all screening exams. The health center's provider will notify participants of their results.

13. Data Analysis

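### Aim 8 counts self-reported screening, collected by the study team that runs the intervention, with no rule that a counted test must follow the session

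*Combined protocol and SAP*

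**What the plan says.** **Entry.** Section 4.1 has staff judge eligibility "as defined below according to self-report on the screening form", and this covers Aim 8. The Aim 8 criteria in 4.9 depend on screening history. For breast cancer, for example, a woman qualifies if she "never had a mammogram OR not had a mammogram within the past 2 years". No record check is mentioned.

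**Follow-up.** Section 12 (Aim 8) introduces the surveys as the means of documenting the intervention's impact on screening: "We will conduct 2 waves of outcomes evaluation surveys: BL and at follow-up (6-8 months post-INT". On who collects the data, it says "Zuni students and staff will administer the surveys". The focus-group paragraph classifies people by whether they report being up to date, and the extra form handed out after each group again only asks the participant.

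**Intervention and reminders.** The session, the reminders, the follow-up calls and the home visits are all described as done by the study team. Reminders stop on the participant's word: "Participants that report completing their appropriate screening will be taken off the reminder call list".

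**Another source.** Section 12 also states "The health center will analyze all screening exams", but no section uses the health center as a source for the outcome.

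**Analysis.** Section 13.2 takes completion of screening as the Aim 8 primary outcome. It models the number of screenings done, offset by the number possible, with Poisson regression, and compares people who do and do not receive the intervention. It names no data source, no verification step, no dating rule and no sensitivity analysis for misreporting.

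**The concern.** Participants are taught that screening matters, are reminded to get it, and are then asked by the same team whether they did. Some people who were not screened may say yes out of courtesy. In addition, a person tested shortly before joining, who was recorded as overdue at entry, could truthfully report that test at follow-up. Without a dating rule it would count as an effect of the session.

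Impact on screening and cost effectiveness are both stated pilot outcomes, and a false completion affects both. The background section says that later studies will use this project's results to design and test interventions, so an inflated uptake figure could carry over into the planning of the next trial.

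**Working it through.** **1. The plan's own figure.** The only Aim 8 design number is the sample size. Section 12 gives 60 men aged 45-75, 60 women aged 45-75 and 30 women aged 21-44: 60 + 60 + 30 = 150, which agrees with section 5.4.1. The documents give no expected uptake, effect size, power or error rate, so every rate below is an assumption.

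**2. Single group.** Let p be true uptake, Se the share of screened people who say yes, and f the share of unscreened people who say yes. Then

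reported uptake = Se × p + f × (1 − p).

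With p = 0.20 and Se = 0.95:

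- f = 0.05: 0.20 × 0.95 + 0.80 × 0.05 = 0.19 + 0.04 = 0.23
- f = 0.15: 0.20 × 0.95 + 0.80 × 0.15 = 0.19 + 0.12 = 0.31

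The excess is 3 to 11 percentage points over 20%, or 15% to 55% in relative terms (3/20 and 11/20).

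Setting Se = 1 isolates the false yes. At p = 0.20, f of 0.05, 0.10 and 0.20 gives 24%, 28% and 36%. With one due test per person that is 150 × 0.80 × f = 6, 12 and 24 false completions. The excess f × (1 − p) shrinks as true uptake rises: at p = 0.40 the reported figures are 43%, 46% and 52%.

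**3. Tests done before the session.** If a share q of people with no test after the session report an earlier one, reported uptake rises by q × (1 − p). This has the same form as a false yes: q = 0.05 at p = 0.20 adds 0.05 × 0.80 = 4 points. Here every answer at follow-up is truthful, so only a dating rule removes it.

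**4. Two groups.** Section 13.2 speaks of treatment arms, although the Aim 8 procedures in section 12 describe no comparison group. For illustration, assume 75 people per group, one due test each, Se = 1 and a two-sided 5% comparison of two proportions. This stands in for the planned Poisson model and does not reproduce it.

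- Unequal misreporting, true uptake 20% in both groups. With f = 0.05 in the comparison group and 0.10 in the taught group, reported uptake is 24% and 28%: ratio 1.17, about an 8% chance of a significant result. With f = 0.05 and 0.20 it is 24% and 36%: ratio 1.50, about 36%.
- Equal misreporting, true uptake 20% and 40%. With f = 0.10 in both groups, reported uptake is 0.20 + 0.10 × 0.80 = 28% and 0.40 + 0.10 × 0.60 = 46%. The ratio falls from 2.00 to 1.64 and power from about 77% to 63%.

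The direction of the bias therefore depends on which comparison is made.

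**5. The reminder motive.** As the survey paragraph of section 12 is written, reminders fall 6 to 8 months after the session at 3-monthly intervals. A two-month window holds about one such contact, and it overlaps the follow-up survey.

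**The case against.** Several stronger readings are tempting, and the documents do not support them.

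- **That the same person teaches, reminds and interviews a participant.** No section says so. The session paragraph does not name who leads it, and project staff appear as educators only in a list of options that the advisory panel might choose. What stands is that one study team does all three and nothing separates the roles.
- **That people will say yes to stop the calls.** About one reminder contact is a weak motive. The longer reminder period elsewhere in section 12 is again only an option. Courtesy reporting does not depend on it.
- **That the errors always inflate the effect.** Courtesy over-reporting at entry would exclude people, nothing shows that payment leads anyone to under-report, and equal misreporting in two groups dilutes the effect.
- **That everyone enters overdue.** The colorectal criteria in 4.9.2 are joined by OR. Read literally, they can admit someone with a colonoscopy in the past 10 years but no stool test in the past year.
- **That test dates are not collected.** The survey forms and eligibility screener are separate files, not shown, and may already ask for them.
- **That the health center could simply confirm the outcome.** Analyzing the exams does not give the study access to the records. A lookup would conflict with 16.2, 16.4 and 16.8, with the anonymity statement in section 18, and with the plan in the checklist section to destroy contact details.

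It is also fair to say that this is a pilot of at most 150 people with feasibility and acceptability among its outcomes, so record verification can reasonably be treated as a preference. That does not excuse leaving the counting rule and the label of the primary outcome open.

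**Conclusion.** The point holds in a limited form. Aim 8 screening status is self-reported at entry. That it is also self-reported at follow-up is an inference from the survey and focus-group paragraphs of section 12, because 13.2 names no source. The study team that intervenes also collects the outcome, and no rule requires a counted test to follow the session.

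In a single-group reading this favors inflated uptake. With a comparison group it can dilute an effect or create one. The size is unknown. The range of 23% to 31% reported against 20% true rests wholly on assumed rates, and it leaves out misreporting at entry. A reader should not conclude that a large bias has been shown, or that one interviewer holds every role.

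**What to change.** 1. For the follow-ups that remain, have the post-intervention survey given by an existing student or staff member who did not deliver that person's session or reminders.
2. State in 13.2 that a test counts as completed only if its reported month and year fall after the session. Add type and date fields if the survey forms lack them.
3. In 13.2 and in reports, call the outcome 'self-reported screening completion'.

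The cost is some rostering, possibly a few survey fields, and a reported uptake that may be lower. Section 12 shows that some follow-up surveys had already been done, so item 1 helps only those remaining. Item 2 removes earlier tests but not an outright false yes, and it relies on recalled dates. Item 3 costs almost nothing.

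Confirmation by the health center, with participant permission, is optional. It would need IRB and tribal IRB modifications, and reconciliation with 16.2, 16.4, 16.8, the anonymity statement in section 18 and the plan to destroy contact details.
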